4.4.1.2 Permitted Therapies under Special Circumstances (Requires Medical Monitor Approval)

- The following are permitted therapies under special circumstance and require Medical Monitor approval:
 - Short-term or intermittent use of medications that may significantly affect cognition (including but not limited to, sedatives, narcotics [e.g., opiates/opioids], hypnotics, anti-psychotic medications, OTC sleeping aids, sedating anti-allergy medications)

These medications should, if possible, be suspended for 2 days or 5 half-lives, whichever is longer, prior to any cognitive assessment, FDG-PET scan, or MRI scan.
- Anti-cholinergic antidepressants, such as tricyclic antidepressants, and benzodiazepines, only if used at low doses that are stable for at least 6 weeks prior to screening, and if deemed medically necessary for the treatment of a non-excluded medical condition
- Non-sedating anti-seizure drugs (e.g., pregabalin) use for a non-seizure indication
- Anticoagulation therapy (e.g., temporary usage during surgery, for treatment of deep vein thrombosis)

In these circumstances, appropriate safety assessments should be made if occurring prior to a lumbar puncture. The investigator should discuss with the Medical Monitor all individual participant cases that require anticoagulant therapy.

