If, during the course of the trial, the investigator determines that the participant has lost capacity to provide informed consent to participate in research, the study partner will be required to accompany the participant to visits involving the study partner. It is strongly preferred that the designated study partner is the same individual throughout the entire study. However, if the study partner role has been reassigned, and the original study partner again becomes available, the role should be reassigned to the original study partner.

If a participant is started on prolonged therapy with a permitted medication known to affect cognitive function (e.g., antidepressants, atypical antipsychotics) after enrollment into the trial, the dose of that medication must be maintained for at least 6 weeks prior to the administration of any cognitive assessments. If a participant is started on a short-term therapy with a permitted medication known to affect cognitive function after enrollment into the trial, that medication must be stopped 2 days or 5 half-lives, whichever is longer, prior to any cognitive, functional, or behavioral assessment. Use of cannabinoids is prohibited for the 24 hours prior to any cognitive assessment.

The cognitive test batteries include a Screening Battery, the API ADAD Composite Cognitive Test Battery, and an Extended Cognitive Battery. Additional functional and behavioral assessments and other self-reported questionnaires will also be administered.

Cutoff scores for some tests may be lower than what is traditionally used in U.S. studies because of differences in population demographics. Assessment scores obtained from participants with low levels of education should be interpreted thoughtfully.

Screening Battery

The Screening Battery consists of the Word List and the MMSE. The scores obtained on these assessments will be used in determining eligibility.

API ADAD Composite Cognitive Test Battery

The API ADAD Composite Cognitive Test Battery was chosen for its sensitivity to measure clinical change in this and other at-risk populations after controlling for practice effects. The battery consists of the Word List, Multilingual Naming Test, MMSE, CERAD Constructional Praxis; and Raven's Progressive Matrices.

Extended Cognitive Test Battery

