Immediately after a participant *discontinues in the first occurrence* from the *crenezumab treatment*, the population-level annualized rate of change will be assumed to be the same as the population-level annualized rate of change in the placebo arm. This approach will likely yield a conservative estimate of the treatment effect. In particular, the model is written as:

$$Y_{ij} = \alpha + (\text{Randomization Factors})_i + u_{0i} + (\beta + u_{1i})t_{ij} + \left(\beta_x \left(t_{ij} I_{t_{ij} \leq t_{i,discon}} + t_{DROP} I_{t_{ij} > t_{i,discon}} \right) \right) I_{x,i} + \epsilon_{ij}$$

where $t_{i,DROP}$ represents the time of *the first occurrence of discontinuation from the crenuzumab treatment* for participant i , and $I_{t_{ij} \leq t_{i,discon}}$ and $I_{t_{ij} > t_{i,discon}}$ are indicator variables similarly defined previously in this document. If a participant has not discontinued from the crenuzumab treatment during Study Period A, then $t_{i,discon}$ is defined as an arbitrarily large number (e.g., 100 with “year” as the unit). The 95% CIs and p-values for estimates in β_x will be presented.

- Analysis using control-based mean imputation
The underlying assumption of this sensitivity analysis is that the missing value mean from the crenuzumab arm is the same or worse than the estimated overall mean from the placebo arm. Consequently, this approach yields a conservative treatment effect estimate in crenuzumab. The details of this approach can be found in Mehrotra et al. (2017). The model setup and more statistical details can be found in [Appendix 3](#).
- Analysis using hypothetical strategy for all intercurrent events, except for the dosing regimen change. The intercurrent events and the handling strategy in this analysis is defined as follows:
 - Events that lead to treatment withdrawal due to an adverse event.
A hypothetical strategy where all values will be censored after the first occurrence of the intercurrent event.
 - Death: A hypothetical strategy where all values will be censored after the occurrence of the intercurrent event.
 - Pregnancy that leads to treatment withdrawal. A hypothetical strategy will be applied where all values will be censored after the occurrence of the intercurrent event.

- Resumption of dosing after treatment discontinuation post-protocol amendment, v8. A hypothetical strategy where all values will be censored after 1 day before the first occurrence of the intercurrent event.

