- Dose change from SC to IV administration. A treatment policy strategy will be applied where all observed values will be used regardless of the occurrence of the intercurrent event.
- Events that lead to treatment interruption or withdrawal due to COVID-19 diagnosis. A hypothetical strategy where all values will be censored after the first occurrence of the intercurrent event.
- *Concurrent use of protocol-defined prohibited medications that can potentially impact cognition (e.g., anti-psychotics, anticonvulsants, benzodiazepines, etc.). A hypothetical strategy will be applied where all values will be censored from the start date of the occurrence of the intercurrent event to 2 days after the occurrence of the intercurrent event.*

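### The sensitivity analysis that censors scores under cognition-affecting medication stops 2 days after an undefined 'occurrence', omitting the 5-half-life limb of the protocol's interval for comparable drugs

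*SAP*

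**What the plan says.** SAP 5.3.4 lists five sensitivity analyses for the primary endpoints. The last is headed "Analysis using hypothetical strategy for all intercurrent events, except for the dosing regimen change". It covers seven intercurrent events. The last of these is described as "Concurrent use of protocol-defined prohibited medications that can potentially impact cognition (e.g., anti-psychotics, anticonvulsants, benzodiazepines, etc". For this event, values are censored from its start date "to 2 days after the occurrence of the intercurrent event". There is no half-life term, and *occurrence* is not tied to the first or the last day of use.

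The protocol speaks in two places about the interval between a short course of a cognition-affecting drug and cognitive testing:

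- Section 4.4.1.2 concerns "Short-term or intermittent use of medications that may significantly affect cognition", which needs Medical Monitor approval: "These medications should, if possible, be suspended for 2 days or 5 half-lives, whichever is longer, prior to any cognitive assessment, FDG-PET scan, or MRI".
- Section 4.5.1.14 concerns short-term therapy with a permitted medication: "that medication must be stopped 2 days or 5 half-lives, whichever is longer, prior to any cognitive, functional, or behavioral assessment".

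For prolonged therapy with a permitted medication, Section 4.5.1.14 has a different rule: "the dose of that medication must be maintained for at least 6 weeks prior to the administration of any cognitive assessments".

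The list of prohibited therapies in Protocol 4.4.1.3 gives no interval. SAP Appendix 1, which records departures from the protocol's planned analyses, does not mention this one.

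**The concern.** A hypothetical strategy asks what the scores would have been without the drug, so the censoring window should last about as long as the drug is expected to influence testing. The trial has its own working answer for short-term use of such drugs: the longer of two limbs. The SAP uses the shorter, fixed limb for every drug. For slowly eliminated drugs, the analysis would start using scores again while the protocol would still have sites wait before testing.

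The undefined *occurrence* adds to this. If a programmer reads it as the start of use, censoring ends 2 days after the first dose even when use continues, and scores taken on the drug stay in.

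The primary estimand (SAP 5.3.2) keeps all values for this event under a treatment policy strategy. This sensitivity analysis is therefore the prespecified check on whether such drugs matter, and an incomplete window weakens that check.

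**Working it through.** The plan states no figure here to reproduce, so the check compares the two rules.

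**Inputs**
- SAP tail after use: 2 days = 48 h (SAP 5.3.4), taking *occurrence* as the end of use, the reading kinder to the SAP.
- Protocol interval: max(48 h, 5 × t½) (Protocol 4.4.1.2 and 4.5.1.14).
- Spacing of cognitive visits: 24 to 28 weeks = 168 to 196 days, midpoint 182 days (Protocol Appendices 2 and 4).
- Half-lives: not given in the documents. Assumed range 10 to 100 h.

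**Formulas**
- Break-even half-life: 48 / 5 = 9.6 h. At or below this the two rules agree.
- Uncensored gap in days: (5 × t½ − 48) / 24.
- Drug remaining at 48 h, assuming first-order elimination: 0.5^(48 / t½). After 5 half-lives it is 0.5^5 = 1/32 = 3.1%.
- Share of episodes with a scheduled visit in the gap, assuming visit dates are unrelated to drug use: gap / visit spacing.

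**Results**

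| Assumed t½ | Protocol interval | Gap | Drug left at 48 h | Share of episodes (196 to 168 days) |
|---|---|---|---|---|
| 10 h | 2.08 days | 0.08 days | 3.6% | 0.04% to 0.05% |
| 12 h | 2.5 days | 0.5 days | 6.2% | 0.26% to 0.30% |
| 24 h | 5.0 days | 3.0 days | 25% | 1.5% to 1.8% |
| 48 h | 10.0 days | 8.0 days | 50% | 4.1% to 4.8% |
| 96 h | 20.0 days | 18.0 days | 71% | 9.2% to 10.7% |
| 100 h | 20.8 days | 18.8 days | 72% | 9.6% to 11.2% |

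At the 182-day midpoint the shares are 0.08 / 182 = 0.05% at 10 h, 3 / 182 = 1.6% at 24 h, and 18.8 / 182 = 10.3% at 100 h. The composite battery is also scheduled at Week 12 (Protocol Appendix 1). For that endpoint, 84-day spacing doubles the 168-day figures over the first 24 weeks only.

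**If *occurrence* means the start of use.** For a course of D days with D above 2, a further D − 2 days of current use go uncensored before the gap above begins. The SAP sentence refers to a start date separately, which favours the end-of-use reading, but it does not say so.

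**The case against.** The strongest objection is that the two documents address different things. The SAP event is use of prohibited drugs. The protocol interval is written for permitted or approved short-term use, and no interval is stated for prohibited drugs. Section 4.4.1.2 also softens its rule to what is possible, although Section 4.5.1.14 makes it mandatory. Both tell sites when to test, and neither says that a score taken inside the interval is invalid. The protocol accepts testing on some of these drugs, such as benzodiazepines or atypical anti-psychotics at a stable dose (4.4.1.1). A site that follows Section 4.5.1.14 would have no score in the gap for permitted short-term drugs.

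All of this stands. A reader might infer that the SAP contradicts the protocol, or that the protocol classes the retained scores as drug-affected. The documents support neither. The interval is borrowed by analogy.

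The analogy is still reasonable. The drug classes overlap: anti-psychotics appear in both Protocol 4.4.1.2 and the SAP's examples, and the SAP also names benzodiazepines, which the protocol handles as permitted or conditionally permitted. The SAP's 2 days equals the first limb of the protocol rule. Nothing in either document suggests that a drug's effect on testing is shorter because the drug is prohibited.

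It is also fair to say that the length of a censoring tail is partly the analyst's judgement, and that the 5-half-life version needs a source of half-lives that neither document supplies. That supports prespecifying the choice and giving a reason.

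**Conclusion.** The point holds as a small improvement. As written, this analysis can keep scores that fall within the only interval the trial states for comparable drugs, whenever the half-life exceeds 9.6 h and a cognitive visit falls in the gap. The meaning of *occurrence* is also open.

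The size depends on assumed half-lives of 10 to 100 h, visits 24 to 28 weeks apart, and visit dates unrelated to drug use. On those assumptions about 0.05% to 11% of episodes could leave one such score in. The upper end needs a half-life near 100 h. The number of episodes is unknown, so the number of scores is unknown too. Nothing in the documents indicates a direction of bias or an imbalance between arms.

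A reader might also infer that the sensitivity analysis fails to estimate its target, or that the trial's main result is exposed. Neither follows. The SAP states which values it censors, and a fixed 2-day tail is a crude approximation to the hypothetical strategy. Only one of seven events in one of five sensitivity analyses is touched. The primary estimand uses every observed value for this event, so the primary tests, alpha and power do not change.

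**What to change.** In SAP 5.3.4, censor values from the start date of use to the longer of 2 days or 5 half-lives after the last recorded use. This also settles *occurrence* by giving it an end date. State that the interval is taken from Protocol 4.4.1.2 and 4.5.1.14 by analogy, and report the number of scores censored by arm. If a flat 2 days is intended, give the reason and still define the end of the event.

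The cost is a sentence or two of SAP wording, a half-life lookup by drug fixed before unblinding, and a few more censored values. Concomitant medications are already recorded in the eCRF (Protocol 4.4.1), so no new data collection is needed.

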5.3.5 Supplementary Analyses for Primary Endpoints

The following supplementary analyses will be performed for the primary endpoints to provide further understanding of the treatment effect.

- Analysis investigating efficacy in SC crenezumab versus efficacy in IV crenezumab: In this analysis, the treatment effect will be assumed to be different between the 2 administration periods. This analysis intends to gain insight on the impact of dose on the treatment effect. Since the IV dose is approximately 4-fold higher than the SC dose, we can use the administration method as a proxy for the dose. In this analysis, the change in administration method is assumed to change the population-level outcome trajectory for participants in the placebo group. For participants in the crenezumab group, the population-level outcome trajectory will also change once an administration method occurs. Furthermore, the switch can only go from SC to IV. In particular, the statistical model is constructed as:

$$Y_{ij} = \alpha + (\text{Randomization Factors})_i + u_{0i} + (\beta + u_{1i})t_{ij} + \beta_p(t_{ij} - t_{i,s})(1 - I_{x,i})I_{t_{ij} > t_{i,s}} + \left((\beta_{SC,x}t_{ij})I_{t_{ij} \leq t_{i,s}} + (\beta_{IV,x}(t_{ij} - t_{i,s}) + \beta_{SC,x}t_{i,s})I_{t_{ij} > t_{i,s}} \right)I_{x,i} + \epsilon_{ij}.$$

In this model, $t_{i,s}$ denotes the switching time for participant i after baseline; if a participant never switched in Study Period A of the study, then $t_{i,s}$ is defined as an arbitrarily large number (e.g., 100 with “year” as the unit). The parameter β_p denotes the effect of the change in administration method for participants in the placebo group. The variables $I_{t_{ij} \leq t_{i,s}}$ and $I_{t_{ij} > t_{i,s}}$ are indicator variables similarly defined as $I_{x,i}$. The annualized treatment benefit of crenezumab by SC is quantified by $\beta_{SC,x}$; the annualized treatment benefit of crenezumab by IV is quantified by $\beta_{IV,x}$. For model simplicity, up to 1 switch is assumed. The 95% CIs and p-values for estimates in $\beta_{SC,x}$ and $\beta_{IV,x}$ will be presented. The point estimates for the SC and IV treatment effect in the RR scale will also be presented.

- Analysis on each component of the API ADAD Composite Cognitive Test total score
To understand the treatment effect on each component of one of the primary endpoints (API ADAD Composite Cognitive Test total score), the same primary analysis model will be run on each component. The 95% CIs and p-values for the treatment effect estimator will be presented. A forest plot will be made.
- To explore whether decline accelerates or decelerates, a quadratic RCRM where leading t^2 terms (treatment and time 2 interaction terms and random quadratic term) are added to the primary analysis model. The covariance matrix of $\{u_{0i}, u_{1i}, u_{2i}\}$ is assumed to be unstructured and all random effect terms are assumed to be independent of the pure error term. Specifically, this model is written as:

$$Y_{ij} = \alpha + (\text{Randomization Factors})_i + u_{0i} + (\beta + \beta_x I_{x,i} + u_{1i})t_{ij} + (\theta + \theta_x I_{x,i} + u_{2i})t_{ij}^2 + \epsilon_{ij}.$$

All statistical inferences as in the primary analysis model along with the point estimates of θ_x and 95% CI will be presented.

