4.10.8 Determination of Sample Size

This study will enroll up to 300 participants: up to 200 participants will be enrolled in the carrier cohort and up to 100 participants will be enrolled in the non-carrier cohort.

Participants in the carrier cohort will be randomized in a 1:1 randomization ratio of active to placebo participants. The study was originally powered to compare the mean change from baseline over 260 weeks in the API ADAD Composite Cognitive Test total score between the crenezumab group and the placebo. Assuming a 25% dropout rate, two-sided testing at an overall 0.05 level, a placebo group CV of 65% for the Week 260 change scores ($=100\% \times$ standard deviation of placebo participant change scores/mean of placebo participant change scores) and 100 participants per arm, the study will have at least 80% power to detect a true effect of 30% reduction of the mean decline in the placebo group.

Participants in the non-carrier cohort will all receive placebo and will be included in the study in order to maintain the genotype blind.

The study was originally powered based on the API ADAD Composite Cognitive Test Battery total score. However, due to concerns about learning effects and general lack of sensitivity to change in a cognitively normal population, before study unblinding, the Sponsor performed a blinded power analysis on the original primary endpoint API ADAD Composite Cognitive Test Battery Total Score and the secondary clinical endpoints. The Sponsor decided to promote the FCSRT Cueing Index from a secondary endpoint to part of a primary endpoint family (along with the API ADAD Composite) due to its favorable statistical properties and clinical relevance as a sensitive measure of episodic memory dysfunction—the hallmark of emerging symptomatic AD and the most commonly observed, early, and consistent neuropsychological marker of AD (Tounsi et al. 1999; Bateman et al. 2012; Caselli et al. 2020) In the SAP, the Sponsor will provide details of the blinded power analysis along with the evidence of type I error control.

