5.10.1.1 Delayed-Start Analyses

The delayed-start analysis will be used for all continuous efficacy endpoints that will be collected in Study Period B and the potential OLE study. Since the potential OLE will not be published by the finalization of this SAP, the description in this section is in general terms and does not focus on any specific endpoint. However, statistical testing will be performed only on the API ADAD Composite Cognitive Test total score and the FCSRT Cueing Index. Other continuous efficacy endpoints, including clinical endpoints, fluid biomarkers, and imaging biomarkers, will be considered exploratory and thus, formal statistical testing will not be done.

Figure 4 illustrates the concept of the delayed-start analysis. As shown in the figure, a treatment effect is assumed in Period A of Study GN28352; the disease progression slope of mutation carriers from the Study Period A crenezumab arm is assumed to be the same in Study Period B and in the OLE; the disease progression slope of mutation carriers from the Study Period A placebo group; however, will have a different slope in Study Period B and in the OLE. The statistical model details can be found in

Appendix 3. To control the type I error within the delayed-start analyses, the fixed testing sequence is specified in the following figure. The α level in each testing is a two-sided 0.05. If at any stage the null hypothesis H_0 is not rejected, then the formal testing procedure will stop.

Figure 4 Illustration of Delayed-Start Analyses Using Data from the Beginning of Period A of Study GN28352 to the End of Study Period B or OLE

[figure not shown]
[figure not shown]

Figure 5 Testing Hierarchy for Delayed-Start Analyses

API = Alzheimer's Prevention Initiative; ADAD = autosomal-dominant Alzheimer's disease; FCSRT = Free and Cued Selective Reminding Task.

Note: For a definition of H0 and H1, please see Section 2.

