$$\lambda[c] = \frac{\left(\hat{V}(\hat{\beta}_x[c]) \right)^2}{\left(\hat{V}_{cren}^{comp} \right)^2 + \left(\hat{V}_{pbo,MAR} \right)^2}.$$

We will then perform the imputation based on $c=0$. This scenario assumes that the mean slope from the participants with missing values from the crenazumab arm is the same as the estimated overall placebo slope. We note that this assumption is already conservative in estimating the treatment effect because it implicitly assumes participants

on treatment will even do worse than an average placebo participant, after dropping out of the study.

DELAYED-START ANALYSIS MODEL FROM SECTION 5.10.1.1

The statistical model for this delayed-start analysis can be written as:

$$Y_{ij} = \alpha + (\text{Randomization Factors})_i + u_{0i} + (\beta + \beta_x I_{x,i} + u_{1i})t_{ij} + (\beta_{x,B/CAST} t_{ij} - \beta_{x,B/OLE} T_i)(1 - I_{x,i})I_{t_{ij} > T_i} + \epsilon_{ij},$$

where β_x quantifies the crenezumab annualized treatment effect in slowing down the disease progression in Period A of Study GN28352 and $\beta_{x,B/OLE}$ quantifies the treatment effect by switching from placebo to crenezumab in Period B of Study GN28352 and the OLE; T_i represents the time of the first endpoint assessment after participant i enters into Study Period B or the OLE.

Due to the common-close design of Study GN28352, mutation carriers will have varied duration of follow-up at the end Study Period of A. To calculate the crenezumab treatment effect at the end of Study Period A, we first calculate the arithmetic mean of duration in Study Period A (last endpoint assessment date – randomization date in Study Period A + 1) among mutation carriers and we call this duration \bar{T}_1 . On average, the treatment benefit in slowing down the disease progression at the end of Study Period A can be written as:

$$\Delta_1 = \beta_x \bar{T}_1.$$

Similarly, we also calculate the arithmetic average of overall duration at the end of the OLE among mutation carriers and we call this duration \bar{T}_2 . The average treatment benefit remained at the end of OLE can be written as:

$$\Delta_2 = (\beta_x - \beta_{x,B/OLE}) \bar{T}_2 + \beta_{x,B/OLE} \bar{T}_1.$$

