Note that both \bar{T}_1 and \bar{T}_2 are treated as constants and are estimated from the data. A non-inferiority test with different margins will be applied ([Liu-Seifert et al. 2015](#)). A 90% CI will be calculated for $\Delta_2 - 50\%\Delta_1$ or $\Delta_2 - 30\%\Delta_1$, depending on the specified margin in the test; if the lower limit of the CI is greater than 0, then the H_0 will be rejected, meaning that by the end of the OLE at least 50% (or 30%) of the treatment effect at the end of Study Period A is preserved.

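### The SC-versus-IV model reports β_IV alone as the IV benefit, although it also fits a placebo slope change β_p after the switch; the IV effect against placebo is β_IV − β_p

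*SAP*

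**What the plan says.** SAP 5.3.5 uses route of administration as a proxy for dose. It states that "the change in administration method is assumed to change the population-level outcome trajectory for participants in the placebo group", and the model carries a term β_p × (time since switch). That term is multiplied by (1 − I_x), so it acts in the placebo arm only. Crenezumab participants have slope increments β_SC before the switch and β_IV after it. The text then says that "the annualized treatment benefit of crenezumab by IV is quantified by" β_IV. It plans 95% CIs and p-values for β_SC and β_IV, and point estimates on the relative-reduction (RR) scale. No contrast involving β_p is planned.

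Elsewhere the comparator is placebo by the same route. SAP 1.2.1 says that matching placebo follows the active routes and regimens. The estimand in SAP 5.3.2 contrasts crenezumab with placebo by SC or by IV and summarises it as a between-arm difference in annualized change.

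For the delayed-start analysis, SAP 5.10.1.1 says the α "level in each testing is a two-sided 0.05". Appendix 3 says "A 90% CI will be calculated for" the retained-benefit quantity, and rejects if the lower limit exceeds 0. Appendix 3 also defines the knot T_i as a quantity that "represents the time of the first endpoint assessment after participant" i enters Period B or the OLE, whereas Δ2 counts the post-switch period from the mean duration of Period A.

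**The concern.** The SAP allows the placebo trajectory to change at the switch but leaves that change out of the comparison. β_IV compares IV crenezumab with the placebo slope as if no switch had occurred. Anything that alters both arms after the switch is then credited to, or charged against, the IV dose.

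The main reason to expect β_p to differ from zero is the SAP's own assumption. Two other statements make a shared late change plausible. The sample size section of the protocol (4.10.8) adds an endpoint "due to concerns about learning effects and general lack of sensitivity to change in a cognitively normal population", and SAP 5.3.5 plans a further model: "To explore whether decline accelerates or decelerates, a quadratic RCRM". Post-switch time is also later time: Protocol 3.2.2 says IV dosing has been offered only since July 2019, against August 2015 for this SC dose.

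At stake is the dose question, which Protocol 3.2 gives as part of the rationale for the common-close design. No other committed analysis separates IV from SC efficacy; the concentration–efficacy analyses in SAP 5.7.4 are optional.

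**Working it through.** The SAP gives no numerical result for this analysis, so there is none to reproduce. The check is algebra on the printed model, followed by illustrations.

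**Slopes implied by the model**

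| | Placebo | Crenezumab | Difference |
|---|---|---|---|
| Before switch | β | β + β_SC | β_SC |
| After switch | β + β_p | β + β_IV | β_IV − β_p |

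The SC readout is correct. The IV readout minus the same-period contrast is β_IV − (β_IV − β_p) = β_p, whatever the variances or switch times.

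**Illustration.** The printed model was fitted by generalized least squares to noise-free means. 84 per arm is the figure used in the simulations of SAP Appendix 2. The rest is assumed: placebo slope −2/yr, true IV benefit +0.6/yr, follow-up 5–8 years, switch at 2.5–5 years, 80% switching, intercept SD 5, slope SD 0.8, residual SD 4, no intercept–slope correlation. SAP 5.3.5 gives no RR formula for this model. The planned RR below carries over the primary-model form of SAP 5.3.3, −β_IV/β; the matched RR is −(β_IV − β_p)/(β + β_p).

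| β_p | β_IV as planned | β_IV − β_p | Planned RR | Matched RR |
|---|---|---|---|---|
| −1 | −0.40 | 0.60 | −0.40/2 = −20% | 0.60/3 = 20% |
| −0.5 | 0.10 | 0.60 | 0.10/2 = 5% | 0.60/2.5 = 24% |
| 0 | 0.60 | 0.60 | 0.60/2 = 30% | 0.60/2 = 30% |
| +0.5 | 1.10 | 0.60 | 1.10/2 = 55% | 0.60/1.5 = 40% |

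With no drug effect and β_p = +0.5, β_IV is 0.50 and the planned RR shows a benefit of 0.50/2 = 25%.

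**Shared curvature, no drug or route effect.** With initial slope −1.5/yr and curvature of −0.05 or −0.10 per yr² in everyone, β_IV comes out at −0.29 or −0.59. β_SC is at most 0.01 and the contrast is 0.01, so the distortion falls on the IV readout.

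**False significance when the drug does nothing.** Normal approximation at 1.96, switch share 30–100%, and four variance sets given as intercept SD, slope SD, residual SD and correlation: (5, 0.8, 4, 0), (5, 1.5, 4, 0), (8, 2, 6, 0), (5, 0.8, 4, 0.3). The β_IV test rejects in 7–19% of trials at |β_p| = 0.25, 12–58% at 0.5 and 32–99% at 1.0. A separate simulation fitted the mixed model with 70% switching, slope SD 1, residual SD 2 and 60 runs per setting. With a shared change of −0.5, the β_IV test rejected in 63% of runs and the contrast in 7%. With +0.5, the figures were 72% and 3%.

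**Delayed start.** Rejecting when the lower limit of a 90% CI exceeds 0 is a one-sided 0.05 test, not a two-sided one. On timing, the first cognitive assessment in Period B is at Week 25 (Protocol Appendices 5 and 6). The model therefore starts the placebo slope change about 24 weeks later than Δ2 does. Suppose placebo switchers gain the same 0.6/yr from their first Period B dose, with visits 24, 52, 76 and 104 weeks after it and the variances of the illustration. The true Δ2 − 0.5Δ1 is then 1.96 and the planned calculation is biased by −0.38. The chance of showing preservation falls from about 82% to 58%.

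**The case against.** The fitted model is not wrong. β_p is estimated and defined, and β_IV has a coherent meaning as IV crenezumab against placebo had nobody switched. The fault lies in the label and in a missing contrast. The analysis is supplementary, meant to give insight, and outside the α graph. Switching is optional and not randomized, so the corrected contrast is also descriptive. All of this stands and limits the consequence. It does not rescue the label, because the SAP's own comparator is route-matched placebo and its stated aim is the effect of dose.

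The evidence that β_p differs from zero is indirect. The learning-effect remark explains an endpoint change, and the quadratic model only explores curvature. That is fair, but the SAP itself assumes that the placebo trajectory changes.

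The sizes are illustrative. Harm appears only at β_p = −1, which is half the assumed placebo slope. The two sets of false-significance figures differ because their assumed variances differ. The error equals β_p only on the slope scale, and the RR formula for IV is an inference. There is also a precision trade-off: with the example standard errors of 0.293 and 0.241, β_IV has the smaller mean squared error when |β_p| is below √(0.293² − 0.241²) ≈ 0.17. That does not make β_IV the right target, since the size of β_p is not known in advance.

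On delayed start, Figure 5 is not shown, so the full hierarchy cannot be checked. Moving the knot to first dosing assumes immediate onset of effect. The conflict in test level and the mismatch in time origin are nevertheless in the text.

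**Conclusion.** The concern holds. As written, the IV readout differs from the effect of IV crenezumab against placebo over the same period by exactly β_p on the annualized scale. A positive β_p overstates the benefit and a negative one understates it. This is algebra and needs no assumed inputs; the RR figures, curvature results and false-significance rates do rest on the assumptions given. β_SC, the primary tests and the key secondary tests are unaffected. It should be fixed because it is the only committed analysis that separates the two doses. The delayed-start points are secondary: the stated test level is contradictory, and the timing mismatch works against showing preserved benefit.

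**What to change.** In SAP 5.3.5, define the IV benefit as β_IV − β_p and report it with its 95% CI and p-value, using a variance that includes the covariance of the two estimates. Removing the factor (1 − I_x) from the β_p term gives the same result directly. State the RR for IV as −(β_IV − β_p)/(β + β_p). Say that switching was optional, so that the contrast is read with caution.

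For the delayed-start analysis, either use a 95% CI or declare the test one-sided at 0.05, and set both T_i and the time origin in Δ2 to the start of Period B dosing.

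The cost is SAP wording and one contrast statement; no new data are needed. The contrast is less precise than β_IV: the ratio of standard errors is 1.08 to 1.34 over the assumed switch shares and variances, for example 0.293 against 0.241 at 80% switching.
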